### 12.8.1 Primary Efficacy Analyses

The primary efficacy endpoint will be analyzed using a Cochran–Mantel–Haenszel (CMH) test stratified by PGA score at Baseline (PGA scores of 2, 3 or 4) based on the ITT population using the multiple imputation approach.

- For each multiple imputation dataset, the CMH option in PROC FREQ will calculate the adjusted estimate of the common relative risk of success (tapinarof/placebo) over all strata with its 95% confidence interval (CI).
- The logit-based version of the estimate and its confidence bounds will be log-transformed and the SE of the estimate of the log(relative risk) will be back-calculated from the log(confidence bounds) by assuming an asymptotic normal distribution.
- The estimates of the log(relative risk) and their standard errors for all the multiple imputation datasets will be input to PROC MIANALYZE to test the null hypothesis that tapinarof is not different from placebo. The p-value of the combined results will be reported for interpretation.
- PROC MIANALYZE will output an overall estimate of the log(relative risk) and its 95% CI. These will be exponentiated to produce an overall estimate of the relative risk and its 95% CI.

Sensitivity analyses in the ITT population will be conducted in which missing values are not imputed, i.e., Observed Cases (OC), or imputed as treatment failures (TF), and efficacy is tested with the CMH statistic as described above. Supporting analyses of the primary endpoint will also be performed

- in the PP population based on OC only,
- in the ITT population with missing values imputed by LOCF,

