10.4.2.1. Primary Endpoint Analyses

The primary efficacy endpoint is proportion of subjects who achieve PGA score of clear (0) or almost clear (1) with a minimum 2-grade improvement from Baseline at Week 12. The primary efficacy endpoint will be analyzed using a Cochran–Mantel–Haenszel (CMH) test stratified by PGA score at Baseline (PGA scores of 2, 3 or 4).

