10.6. Handling of Missing Data

Every effort will be made to collect complete data at all visits.

The primary method of handling of missing data will utilize Multiple Imputations (MI). For sensitivity analysis, Treatment Failure (TF) will be imputed for missing data.

For the MI model, 100 imputations will be generated using PROC MI of SAS. Fully Conditional Specification (FCS) model using the regression method will be used with the response (eg, PGA score) at prior post-baseline visits, baseline strata, and treatment group as covariates, The ROUND and MINIMUM options will be utilized to ensure imputed values are non-negative integers. The seed to be used is 20180330. The results of the 100 analyses will be transformed into a normal statistic and combined into a single analysis using PROC MIANALYZE.

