#### Imputation of Missing Efficacy Data

The primary method of handling of missing efficacy data will utilize Multiple Imputations (MI). Last observation carried forward (LOCF) method will be used as supportive analysis of the primary and secondary endpoints. For sensitivity analysis of the primary and secondary endpoints, missing data will be imputed as Treatment Failures (TF). Only missing data up to Week 12 will be imputed. Missing data at the Week 16 Follow-up visit will be analyzed as Observed Cases (OC) only.

**MI:** For the MI model, 100 imputations will be generated using PROC MI of SAS. Fully Conditional Specification (FCS) model using the regression method will be used with the response (e.g., PGA score) at prior post-baseline visits, baseline PGA score, baseline value of the corresponding endpoint, and treatment group as covariates, The ROUND and MINIMUM options will be utilized to ensure imputed values are non-negative integers. The seed to be used in all MI model is 20180330.

One set of MI datasets will be generated for the PGA scores, PASI scores and %BSA results separately. Response status (Yes, No) will be derived from the imputed scores in each MI dataset. Analysis of each primary, secondary and exploratory outcome will then be performed for each of the relevant MI datasets. The results of the 100 analyses will be transformed into a normal statistic and combined into a single analysis using PROC MIANALYZE.

Example SAS code for the PGA scores is as follows:

```
PROC MI DATA = PGA1 OUT = PGA2 SEED = 20180330 NIMPUTE = 100 NOPRINT;  
  CLASS TRTPN BASEPGA;  
  FCS LOGISTIC(BASEPGA = TRTPN / DETAILS);  
  FCS REG(PGA3 = TRTPN BASEPGA / DETAILS);  
  FCS REG(PGA4 = TRTPN BASEPGA PGA3 / DETAILS);  
  FCS REG(PGA5 = TRTPN BASEPGA PGA3 PGA4 / DETAILS);  
  FCS REG(PGA6 = TRTPN BASEPGA PGA3 PGA4 PGA5 / DETAILS);  
  VAR TRTPN BASEPGA PGA3-PGA6;  
RUN;
```

The imputation models may be modified based on the actual data if there is an issue in model convergence.

**LOCF:** The last observed value will be carried forward for any subsequent missing values. Baseline values will not be carried forward.

**TF:** missing data will be imputed as treatment failures for responder endpoint.

Missing functional outcomes, quality of life endpoints or safety endpoints will not be imputed.

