## **12.7 Efficacy Endpoints**

### **12.7.1 Primary Efficacy Endpoint**

The primary efficacy endpoint is the proportion of subjects who achieve a Physician Global Assessment (PGA) treatment response, defined as a PGA score of clear (0) or almost clear (1) with a minimum 2-grade improvement from Baseline at Week 12.

The PGA is a static 5-point assessment of overall disease severity, as determined by the Investigator, ranging from 0 (clear) to 4 (severe).

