### **12.8.2 Secondary and Exploratory Efficacy Analyses**

The same methods as discussed for the primary analyses will be used to analyze all dichotomized and continuous secondary endpoints. The secondary efficacy endpoints will be tested sequentially in the order listed. Testing will stop if non-significance (2-sided  $p \geq 0.05$ ) is observed as described in Section 11.6.

Other exploratory efficacy endpoints will be analyzed using CMH test for proportions, and analysis of covariance (ANCOVA) model for continuous variables. CMH tests will be stratified by baseline PGA score, and ANCOVA models will include baseline PGA score as a covariate (2, 3 or 4), and baseline value of the endpoint as a continuous covariate. For proportions, the same MI approach describe above will be taken to deal with missing data. For continuous variables, the standard MI procedures for ANCOVA will be followed. Least squared means of treatment difference (tapinarof – placebo) along with the 95% CI will be reported.

Time to achieving a PGA success will be analyzed with the Kaplan Meier method in the ITT population based on Observed Cases. Treatment groups will be compared using a log-rank test. Estimates of median time to response from Kaplan Meier distribution will be computed. A Kaplan-Meier figure will also be generated.

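### The primary p-value labelled CMH is a Wald test on the pooled logit relative risk, a pre-specified but conservative choice that costs a few power points at 35% vs 20% and nothing material at 40% vs 15%

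*SAP*

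**What the plan says.** Protocol 10.4.2.1 says that the primary endpoint "will be analyzed using a Cochran–Mantel–Haenszel (CMH) test stratified by PGA score at Baseline". SAP 12.8.1 repeats this and then gives the steps. In each imputed dataset, PROC FREQ supplies a common relative risk over the baseline PGA strata. "The logit-based version of the estimate and its confidence bounds will be log-transformed", and a standard error is back-calculated from the bounds. The log relative risks and standard errors go to PROC MIANALYZE. "The p-value of the combined results will be reported for interpretation".

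Both documents announce a transformation before pooling. Protocol 10.6 states: "The results of the 100 analyses will be transformed into a normal statistic and combined into a single analysis using PROC MIANALYZE". SAP 9 says the same.

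For the observed-case (OC) and treatment-failure (TF) analyses, SAP 12.8.1 says that "efficacy is tested with the CMH statistic as described above". SAP 12.8.2 extends the approach: "The same methods as discussed for the primary analyses will be used to analyze all dichotomized and continuous secondary endpoints". SAP 7 gives power above 99% at 40% vs 15% and above 94% at 35% vs 20%, from a Fisher exact calculation that it calls conservative.

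**The concern.** The CMH chi-square never enters the primary p-value. The p-value comes from an inverse-variance relative risk, whose stratum weights are estimated from the same responder counts that it averages. SAP 6 limits PGA 2 and PGA 4 to about 10% each, so two of the three strata are small and their weights are unstable.

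Three things are at stake:
- some power in the SAP's own fallback scenario;
- whether the power statement describes the test that will be run;
- whether the OC and TF analyses use the CMH chi-square or the logit relative risk, since the phrase about the CMH statistic described above can be read either way.

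**Working it through.** **Inputs from the documents.** 500 subjects, 2:1 (333 vs 167); two-sided 0.05; 40% vs 15% and 35% vs 20% (SAP 7); strata of about 10/80/10% (SAP 6). Ten percent of 500 is 50, or about 33 vs 17 at 2:1. The moderate stratum is 400, or 267 vs 133.

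**Assumptions.** The documents give no response rates by stratum and no rule for zero cells. Stratum rates are varied below. Strata with a zero cell either get 0.5 added or are dropped (results for dropping in brackets).

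**The SAP's own figure.** Enumerating the two-sided Fisher exact test at 333 vs 167 gives above 99.9% at 40/15 and 93.8% at 35/20. The first statement reproduces. The second is just missed by its own method; the pooled z test gives 94.5%.

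**The statistics.** In a stratum with a of n1 tapinarof responders, b of n0 vehicle responders, and N = n1 + n0:
- logit: log RR = log[(a/n1)/(b/n0)], weight w = 1/(1/a − 1/n1 + 1/b − 1/n0), z = Σ(w·log RR)/√Σw;
- MH: RR = Σ(a·n0/N)/Σ(b·n1/N), with Greenland-Robins variance of the log;
- CMH: the score chi-square without continuity correction.

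**Why the logit version leans against tapinarof.** Take illustrative counts in a 33 vs 17 stratum, where 17 × 0.20 = 3.4 vehicle responders are expected, with 12 tapinarof responders:
- 2 vehicle responders: RR = (12/33)/(2/17) = 3.09; w = 1/(0.083 − 0.030 + 0.500 − 0.059) = 2.0
- 5 vehicle responders: RR = (12/33)/(5/17) = 1.24; w = 1/(0.083 − 0.030 + 0.200 − 0.059) = 5.2

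The less favourable chance result gets about two and a half times the weight.

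**Power at 35% vs 20%, complete data (%).** Simulated, 200,000 to 400,000 trials per row; Monte Carlo standard error about 0.04 point at 91.5% with 400,000. Power counts significance in favour of tapinarof.

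| Vehicle rate mild/moderate/severe | Effect | CMH | MH | Logit | MH − logit |
|---|---|---|---|---|---|
| 20/20/20 | RR 1.75 (same as +15 points) | 94.5 | 93.9 | 91.5 (91.3) | 2.4 |
| 5/23.75/5 | RR 1.75 | 95.6 | 94.9 | 94.3 (93.7) | 0.6 |
| 10/22.5/10 | RR 1.75 | 95.0 | 94.3 | 93.1 (92.5) | 1.2 |
| 15/21.25/15 | RR 1.75 | 94.7 | 94.0 | 92.2 (91.8) | 1.8 |
| 30/20/10 | RR 1.75 | 94.9 | 94.3 | 92.3 (92.0) | 2.0 |
| 30/17.5/30 | RR 1.75 | 95.0 | 94.3 | 91.8 (91.8) | 2.5 (2.6 unrounded) |
| 30/20/10 | +15 points | 94.7 | 94.0 | 90.8 (90.2) | 3.2 |
| 27/18/27 | +15 points | 94.6 | 93.9 | 90.8 (90.8) | 3.1 |
| 6/23/11 | +15 points | 94.8 | 94.2 | 90.8 (89.2) | 3.4 |
| 5/23.75/5 | +15 points | 95.1 | 94.5 | 90.3 (87.9) | 4.2 |

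In the last row, dropping zero-cell strata gives 94.5 − 87.9 = 6.6 points. The two 5/23.75/5 rows show that low rates in the small strata do not settle the size of the loss. SAP 12.7.1 requires "defined as a PGA score of clear (0) or almost clear (1) with a minimum 2-grade improvement from Baseline at Week 12", so a PGA 2 subject must reach 0. That may make rates low there, yet the loss is 0.6 or 4.2 points depending on how the effect varies across strata.

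**Power at 40% vs 15%.** All three statistics are above 99.9%.

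**Null, 20% in every stratum.** The tail favouring tapinarof is 2.4% for CMH, 2.1% for MH and 1.4% for logit, against 2.5% nominal. Two-sided rates are 5.0%, 4.8% and 4.4%.

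**The case against.** The strongest reply is that nothing is hidden. A reader might infer an undisclosed switch away from the protocol's test. The documents do not support that: SAP 12.8.1 spells out every step, and Protocol 10.6 and SAP 9 both announce a normal statistic before pooling. A statistician could program the primary test without guessing. This stands, and it limits the point to a label and a choice of estimate.

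Second, pooling the MH log relative risk is also a Wald test, so it does not by itself cure the label. This stands too, and the fix therefore includes renaming. The relevant gain is against MH, which is smaller than the gap to CMH.

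Third, a reader might blame the logit choice for the whole shortfall from 94%. Exact Fisher and MH under equal stratum rates also fall just short, at 93.8% and 93.9%, so part of it is rounding in SAP 7.

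Fourth, a reader might infer a large loss for PASI-90. At an assumed 15% vs 5% the logit test has 89.8% (85.7% with zero-cell strata dropped) against 94.8% for CMH. At 20% vs 5% it has 99.6% (99.2%) against 99.9%, under 1 point lower. The documents give no PASI-90 rates, so the first figure is only an illustration.

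**Conclusion.** The point holds as a minor to moderate one. The primary p-value is a Wald test on the pooled logit log relative risk, and it is conservative towards tapinarof. At 35% vs 20% with complete data, its loss against MH is 0.6 to 2.6 points under a common relative risk of 1.75. Under a constant 15-point difference it is about 3 to 4 points, or up to about 7 if zero-cell strata are dropped. Both ranges rest on assumed stratum rates, and the documents do not say which effect pattern to expect.

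The documents do not support reading this as an underpowered trial or an inflated error rate: there is no material loss at the design rates, and the null rejection rate is below nominal. These are not power figures for the planned analysis under multiple imputation. That would need a missingness mechanism and correlations between visits, which the documents do not give.

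The ambiguity about the OC and TF statistic stands whatever the power.

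**What to change.** 1. In SAP 12.8.1, replace the logit-based version of the common relative risk with the Mantel-Haenszel version, which PROC FREQ prints in the same output. Describe the p-value as a Wald test on the pooled MH log relative risk, stratified by baseline PGA. Estimate, interval and p-value then agree.
2. State that this statistic is used for the MI, OC, TF, LOCF and PP analyses and for the dichotomous secondary endpoints (PASI-75, PGA 0 or 1, PASI-90). This settles what the CMH statistic described above means.
3. In SAP 7 and Protocol 10.2, restate the 35/20 power as about 94% (93.8% by Fisher, 93.9% by MH under equal stratum rates and complete data). If the logit test is kept, name it as such and give about 91 to 92% under equal stratum rates and complete data.

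The cost is a dated SAP amendment before unblinding, with a short justification because the primary test and three secondary tests change, and a slightly lower stated power. Sample size and data collection do not change.

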### **12.8.2 Secondary and Exploratory Efficacy Analyses**

The same methods as discussed for the primary analyses will be used to analyze all dichotomized and continuous secondary endpoints. The secondary efficacy endpoints will be tested sequentially in the order listed. Testing will stop if non-significance (2-sided  $p \geq 0.05$ ) is observed as described in Section 11.6.

Other exploratory efficacy endpoints will be analyzed using CMH test for proportions, and analysis of covariance (ANCOVA) model for continuous variables. CMH tests will be stratified by baseline PGA score, and ANCOVA models will include baseline PGA score as a covariate (2, 3 or 4), and baseline value of the endpoint as a continuous covariate. For proportions, the same MI approach describe above will be taken to deal with missing data. For continuous variables, the standard MI procedures for ANCOVA will be followed. Least squared means of treatment difference (tapinarof – placebo) along with the 95% CI will be reported.

Time to achieving a PGA success will be analyzed with the Kaplan Meier method in the ITT population based on Observed Cases. Treatment groups will be compared using a log-rank test. Estimates of median time to response from Kaplan Meier distribution will be computed. A Kaplan-Meier figure will also be generated.

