7.3. Double-Blind, Vehicle-Controlled Phase

Subjects will return to the study site at Weeks 2, 4, 8, and 12 and will be contacted by phone at Weeks 6 and 10 of the double-blind phase of the study.

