7.3.1. Visit 3; Week 2 (Day 15 ±2 Days)

The following procedures and assessments will be performed at Visit 3:

- Vital signs
- PGA score
- %BSA affected calculation (performed before PASI)
- PASI
- LTS
- PSD

- Peak Pruritus-NRS
- AE recording
- Concomitant medication recording
- Collect and dispense subject diaries
- Review subject diaries for treatment compliance
- Collect and dispense study drug
- Review instructions on how to apply study drug
- Study drug application under supervision

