7.3.2. Visit 4; Week 4 (Day 29 ±2 Days)

The following procedures and assessments will be performed at Visit 4:

- Urine pregnancy test (females of child-bearing potential)
- Brief physical examination
- Vital signs measurement
- Photography of a representative area of the subject's disease area (optional; at a subset of study sites)
- Blood sample collection for PK analysis (subset of sites and subjects)
- Blood sample collection for clinical laboratory tests
- PGA score
- %BSA affected calculation (performed before PASI)
- PASI
- LTS
- DLQI
- SF-36
- PSD
- Peak Pruritus-NRS
- AE recording
- Concomitant medication recording
- Collect and dispense subject diaries
- Review subject diaries for treatment compliance
- Collect and dispense study drug
- Review instructions on how to apply study drug
- Study drug application under supervision

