7.3.3. Visit 5; Week 8 (Day 57 ±2 Days)

The following procedures and assessments will be performed at Visit 5:

- Urine pregnancy test (females of child-bearing potential)
- Brief physical examination

- Vital signs measurement
- Photography of a representative area of the subject's disease area (optional; at a subset of study sites only)
- PGA score
- %BSA affected calculation (performed before PASI)
- PASI
- LTS
- PSD
- Peak Pruritus-NRS
- AE recording
- Concomitant medication recording
- Collect and dispense subject diaries
- Review subject diaries for treatment compliance
- Collect and dispense study drug
- Review instructions on how to apply study drug
- Study drug application under supervision

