## **3. STUDY DESIGN**

This is a double-blind, randomized, vehicle-controlled, Phase 3, multicenter study to evaluate the efficacy and safety of topical tapinarof cream, 1% compared with vehicle-control cream in adults with plaque psoriasis.

Following a 34-day screening period, eligible subjects will be randomized at a 2:1 ratio to receive once daily treatment with tapinarof cream, 1% or vehicle cream. Subjects will return to the clinic at Weeks 2, 4, 8, and 12 for efficacy and safety assessments. Additionally, subjects will be contacted by phone at Weeks 6 and 10 to assess adverse events (AEs) and concomitant medications, to review study drug administration instructions, and to confirm subject's continued participation in this study. Study drug will be dispensed to subjects during the clinic visits and will be administered at home between clinic visits as instructed by site personnel. Subjects will

be instructed to apply study drug once daily to all affected areas, including newly appearing lesions and lesions/areas that improve during the study. Subjects will apply sufficient study drug to cover completely each lesion with a thin layer of study drug and will record the time of study drug application in a daily diary provided by the study site. (Note that subjects are allowed, but not required, to treat fingernails, toenails, palms, soles, and scalp lesions with study drug; however, efficacy analyses will not include assessment of improvement of psoriasis in these areas.) Subjects will be instructed to maintain the dosing time chosen at the beginning of the study for their full study participation. At the phone contacts at Weeks 6, 10, and 14, subjects should be reminded to complete their daily diary and bring it with them to the next clinic visit.

At the end of 12 weeks of treatment in this study, subjects will have the option to enroll in a separate open-label long-term safety and efficacy study for an additional 40 weeks of treatment. Subjects who choose not to participate in the open-label long-term study, who fail to qualify for participation in the open-label long-term study, or who qualify to participate in the open-label long-term study but ultimately elect not to enroll in that study, will complete a Follow-up Visit approximately 4 weeks (Week 16 visit) after the end of treatment in this study. Subjects who withdraw from the study before Week 12 will complete an Early Termination Visit.

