### **12.7.3 Exploratory Efficacy Endpoints**

The exploratory endpoints to further characterize the efficacy of tapinarof cream, 1% compared with vehicle control over time are:

- Time (days) to achieving a PGA treatment response, defined as days from date of first dose until achieving a PGA score of 0 or 1 with a minimum 2-grade improvement from Baseline. Subjects who have no PGA response will be censored at the date of their last PGA assessment.
- Proportion of subjects with a PGA score of 0 or 1 at Weeks 2, 4, and 8
- Proportion of subjects who achieve a PGA treatment response at Weeks 2, 4, and 8
- Mean absolute and percent change in PASI score from Baseline to Weeks 2, 4, 8, and 12
- Proportion of subjects with  $\geq 50\%$  improvement in PASI score (PASI-50) from Baseline to Weeks 2, 4, 8, and 12
- Proportion of subjects with  $\geq 75\%$  improvement in PASI score (PASI-75) from Baseline to weeks 2, 4, and 8
- Proportion of subjects with  $\geq 90\%$  improvement in PASI score (PASI-90) from Baseline to weeks 2, 4, and 8
- Mean change in %BSA affected from Baseline to Weeks 2, 4, and 8
- Mean % change in %BSA affected from Baseline to Weeks 2, 4, 8, and 12.

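### Time to PGA response is analysed as if the detection visit were the exact response day. The Kaplan-Meier median can be up to 28 days late if it is reached, and at the planned rates the end of the curve can be inflated enough to print a false median.

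*SAP*

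**What the plan says.** SAP 12.7.3 lists time to PGA response as an exploratory endpoint, "defined as days from date of first dose until achieving a PGA score of 0 or 1 with a minimum 2-grade improvement from Baseline". Its censoring rule is: "Subjects who have no PGA response will be censored at the date of their last PGA assessment". SAP 12.8.2 analyses it by Kaplan-Meier in the ITT population on observed cases, with a log-rank test, a figure and a median: "Estimates of median time to response from Kaplan Meier distribution will be computed". The table in SAP 12.8 lists no sensitivity analysis for it.

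On the schedule, Protocol 7.3 says: "Subjects will return to the study site at Weeks 2, 4, 8, and 12". Protocol 7.3.1 to 7.3.4 put these visits at Days 15, 29, 57 and 85, each ±2 days. Weeks 6 and 10 are phone contacts without PGA. PGA is also scored at Week 16 (Day 113 ±4, only for subjects who do not enter the long-term study) and at early termination. SAP 11.4 also provides for unscheduled visits.

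Neither document mentions interval censoring, says how an unreached median will be reported, or says whether Week 16 PGAs count as events.

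**The concern.** A response first seen at a visit began at some time after the previous PGA. The plan knows only that interval but enters its right end as an exact day. This has two consequences:

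- The curve can step only where PGAs are done. If the median is reached, it is read at the visit after the true one.
- Within a visit window, a non-responder seen early is censored, while a subject not yet seen stays at risk. The subject still at risk carries four weeks of unobserved response, and Kaplan-Meier treats the two as exchangeable. The estimate then climbs too far at the last visit.

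At stake are the reported median and the Kaplan-Meier figure, which are the trial's direct description of onset in days.

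**Working it through.** **Plan figures.** The documents give no figure for this endpoint. The only anchor is the sample-size section (Protocol 10.2, SAP 7): 333 and 167 subjects, 40% vs 15% response at Week 12 (alternative 35% vs 20%), and up to 25% loss. These inputs reproduce the stated power for the primary endpoint. The first pair gives over 99.9% (stated > 99%). The second gives 93.8% by exact Fisher enumeration, or 94.5% by the pooled normal formula (stated > 94%).

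**Time scale.** Days below are days after first dose, that is study day minus 1. Nominal visits are at 14, 28, 56 and 84.

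**1. Interval widths.** Nominal gaps are 14, 28 − 14 = 14, 56 − 28 = 28 and 84 − 56 = 28. At the window edges they are 16, 30 − 12 = 18, 58 − 26 = 32 and 86 − 54 = 32.

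**2. Is a median expected?** Assume exponential time to first response, with proportion F responding by day 84. The median is then 84 × ln 2 / −ln(1 − F).

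- F = 0.40: 58.22 / 0.5108 = 114 days.
- F = 0.15: 58.22 / 0.1625 = 358 days.

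Both lie beyond Week 12. With every visit on its nominal day, simulation reached a median in 0% of runs in either arm.

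**3. Shift if a median is reached (nominal days).**

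| F by day 84 | True median | Kaplan-Meier median | Shift |
|---|---|---|---|
| 0.60 | 63.5 | 84 | +20.5 |
| 0.70 | 48.4 | 56 | +7.6 |
| 0.80 | 36.2 | 56 | +19.8 |
| 0.865 | 29.1 | 56 | +26.9 |

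The nominal ceiling is 28 days after Week 4 and 14 days before it. The mean delay among responders by Week 12 is about 11.5 days. All four rates are well above the planned 40%.

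**4. End of the curve at the planned 40%, using actual dates.** The proportion without response at Week 8 is 0.6^(2/3) = 0.711. The chance of response in the last interval is q = 1 − 0.6^(1/3) = 0.157. Suppose attendance is even over days 82 to 86, q is the same on each day, and there are no Week 16 data. Each day one fifth of the group is seen. Responders count as events and the rest are censored, so the risk set shrinks to 5/5, 4/5, 3/5, 2/5 and 1/5.

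| Day | Kaplan-Meier factor |
|---|---|
| 82 | 1 − q/5 = 0.969 |
| 83 | 1 − q/4 = 0.961 |
| 84 | 1 − q/3 = 0.948 |
| 85 | 1 − q/2 = 0.922 |
| 86 | 1 − q = 0.843 |

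The product is 0.686. The curve ends at 1 − 0.711 × 0.686 = 0.51, and a median is printed at day 86. The correct factor is the single 0.843, giving 1 − 0.711 × 0.843 = 0.40. For vehicle (q = 0.053, 0.85^(2/3) = 0.897), the same arithmetic gives 0.21 instead of 0.15, and no median.

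**5. Simulation.** With 333 subjects, 25% loss, dates spread over ±2 days and no Week 16 data, the tapinarof curve ended at 0.52 to 0.55. A median near day 86 appeared in 66% to 74% of runs, against a true 114 days. Varying the visit spread and letting 0 to 30% of non-responders have a Week 16 PGA widened this to 0.44 to 0.57, with a false median in 2% to 81% of runs. Week 16 data reduce the error because those non-responders stay in the risk set. At 35% response, a false median appeared in 0% to 46% of runs.

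**The case against.** The strongest reply is that this changes little.

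- The endpoint is exploratory and outside the fixed sequence in SAP 11.6.
- PGA response at Weeks 2, 4, 8 and 12 is already planned by multiple imputation. It shows onset by visit without a day-precise claim.
- Dating response at first documentation is a coherent definition, and a one-line label would make that clear.
- SAP 11.4 analyses endpoints by nominal visit.

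The first two points stand and hold the severity down. The label does not cure the second error: the proportion with a documented response by day 86 is still 40%, and step 4 returns 0.51. SAP 11.4 assigns assessments to visits, but the endpoint is defined in days between dates, with censoring at a date.

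A reader might also draw stronger conclusions that the documents do not support:

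- **The median will be reported up to 28 days late.** This needs cumulative first response above 50%. First response can exceed the Week 12 rate, because some subjects respond and later lose response. At the planned 40%, that would have to be 10 or more percentage points of subjects.
- **The error is always late.** Near Week 12 it can be early: day 86 against a true 114.
- **The treatment comparison is biased.** Both arms share one schedule, so the visit spacing makes the log-rank test coarser and tied, not biased.
- **The median can fall only on the four visit days.** Early-termination, unscheduled and Week 16 PGAs can add other steps, and a missed visit can widen an interval beyond 28 days.
- **The dose rationale depends on this endpoint.** Protocol 1.2 compares onset at 1% and 0.5% in earlier work, and this trial has no 0.5% arm.

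**Conclusion.** The concern holds as a minor point about an exploratory endpoint. Visit-detected responses are analysed as exact event days. A median that is truly reached moves to the next visit, nominally up to 14 days late before Week 4 and up to 28 days late after. At the planned rates none should be reached by Week 12, but the planned method can still show the tapinarof arm at about 0.52 to 0.55 instead of 0.40 and print a false median near day 86.

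These sizes rest on an exponential response time, 25% loss, dates spread over the ±2-day windows and no Week 16 data. The documents give the windows and the loss. The response shape, the visit spread and the Week 16 share are assumptions, and the size of the error is sensitive to the last two.

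**What to change.** In SAP 12.8.2, analyse time to PGA response as interval-censored:

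- Left bound: the last non-response PGA, or first dose if there is none.
- Right bound: the first response PGA.
- No response: right-censored at the last PGA.
- Method: the nonparametric interval-censored estimate and the generalized log-rank test (PROC ICLIFETEST).
- Reporting: give the median as a visit interval, for example over 56 to 84 days, or as not reached by Week 12.
- Week 16: state whether these off-treatment PGAs count.

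Place scheduled PGAs on their nominal visit day when setting the bounds. With bounds at actual dates, the estimate can still rise somewhat too far on the last window days, because it cannot decrease and few subjects are seen then. A simulation check showed most of the inflation removed, but not all. With nominal bounds the last step is the single factor in step 4, and the curve ends at 0.40.

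The cost is SAP wording and one SAS procedure. The small downside is a median given as an interval instead of a day.
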